1.0 SUMMARY OF STUDY (Abstract with a maximum of 300 words)

The ideal local anesthetic (LA) solution for activation of a labor epidural would be one that provides rapid pain relief with minimal side effects such as hypotension and motor blockade. Commonly used LA in obstetrics includes bupivacaine and lidocaine. Due to either slow onset (bupivacaine)¹ or a higher incidence of hypotension (lidocaine)² neither meet the criteria for the ideal LA. This is where the thought of combining the two LA solutions arises. Maybe a 1:1 mix will produce a faster onset than bupivacaine with a lower incidence of hypotension than lidocaine.

We hypothesize that lidocaine will achieve a T₁₀ level the fastest when compared to bupivacaine and bupivacaine plus lidocaine. The bupivacaine plus lidocaine onset of action will not be significantly faster when compared to bupivacaine. Given the concentration of the bupivacaine, less hypotension and motor block will be present when compared to the lidocaine and bupivacaine plus lidocaine. The bupivacaine plus lidocaine will offer no increased benefit of having a faster onset with less hypotension or motor blockade than either LA solution alone.

We will conduct a prospective, randomized, double-blind study on 45 patients receiving a lumbar epidural for labor analgesia. After a negative test dose, the anesthesia provider will administer the randomized LA via epidural catheter: 10 mL 0.125% bupivacaine, or 10 mL 1% lidocaine, or 5 mL 0.125% bupivacaine plus 5 mL 1% lidocaine. The investigator will assess the patients sensory level to pin prick and ice, degree of motor block, blood pressure, heart rate, and fetal heart rate at intervals of 0, 5, 10, 15, and 20 minutes. Primary outcome will be the time to achieve a T₁₀ level. Secondary outcomes include the total spread of the block, onset and degree of motor block, incidence of hypotension and need for vasopressor therapy, and fetal well-being.

2.0 BACKGROUND & RATIONALE

The most common and effective method for controlling labor pains is a local anesthetic infusion through a lumbar epidural.¹ To achieve adequate pain control during the first stage of labor – onset of contractions to complete cervical dilation – nerve fibers up to the T₁₀ dermatome must be anesthetized.¹ When a patient is in active labor and an epidural catheter is placed, the anesthesiologist must activate the epidural by administering LA through the epidural to promote spread of the LA in the epidural space to anesthetize the nerve fibers involved in the conduction of labor pains. The ideal LA to achieve this goal is one that would allow for the fastest onset to achieve quick pain relief with the fewest side effects. Common side effects of LA used in labor epidurals include maternal hypotension and motor blockade.³

Two commonly used LA to provide labor analgesia are bupivacaine and lidocaine. When low concentrations – 0.125% bupivacaine and 1% lidocaine – are used for labor analgesia, both of these LA can be administered safely with very little concern of major adverse effects associated with LA toxicity. However, more common side effects such as maternal hypotension requiring vasopressor therapy and motor blockade can often occur.³

Though both are amide LA, bupivacaine and lidocaine display different properties that give each an advantage in certain situations. Lidocaine's onset of action is faster than that of bupivacaine's (5-15 vs. 10-20 minutes for epidural injection).¹ Whereas bupivacaine has a longer duration of action (180-300 vs. 60-180 minutes).¹ Through a sympathetically mediated veno- and vaso-dilation, both LA commonly cause hypotension. Although the time to develop hypotension was not noted, several studies have noted a higher incidence of hypotension with the administration of epidural lidocaine vs. bupivacaine.^{2,4}

Despite the novel idea that combining these two LA in an effort to achieve the ideal properties of each – lidocaine's faster onset and bupivacaine's tendency towards less hypotension – only a few studies have been published on this topic. Two articles assessing the onset of action of bupivacaine, lidocaine, and a combination of both for local infiltration found no difference in onset of action.^{5,6} One article did note a significant decrease in time to onset of sensory and surgical block in patients receiving bupivacaine plus chloroprocaine (ultra-fast acting LA) vs. bupivacaine in patients undergoing an axillary block.⁷ Two studies looking at adding lidocaine to a bupivacaine spinal in an effort to achieve the opposite effect – decreasing the duration of the spinal – had conflicting results with one showing a shortened duration while the other showing no difference. Both studies report no difference in onset of action.^{8,9} In patients requiring conversion of a labor epidural to a surgical block, one study found no difference in time to achieve a T₄ surgical level in the lidocaine, bupivacaine, or combination groups.¹⁰ In non-pregnant patients undergoing lower abdominal surgery, Seow et al. showed no difference in development of a sensory block but the onset of a complete motor block was significantly faster in the 1:1 bupivacaine:lidocaine concentration group.¹¹ The one study that was found assessing time of onset and extent of sensory and motor block in parturients receiving a labor epidural found no significant difference comparing bupivacaine to a bupivacaine and lidocaine combination.³

Given that there is limited and conflicting evidence for the usefulness of the bupivacaine and lidocaine mixture especially as it relates to labor epidural activation, we hope to readdress these questions in an effort to determine whether or not the LA combination offers any distinct advantage over the individual LA. In contrast to Sinatra et al's study, we intend to determine the time it takes to achieve an adequate level (T₁₀) for labor analgesia, the total spread of local anesthetic (both caudal and rostral), and the time it takes to develop hypotension – not just the overall incidence – as these factors will be important in determining the most optimal LA solution to activate a labor epidural. We will also reevaluate the degree of motor block, as patients in Sinatra's study received a much higher concentration of bupivacaine (0.5%) than we use for epidural activation (0.125%). With the results of our study, we hope to recommend a LA solution that will allow for the fastest pain relief in the laboring mother with the fewest side effects.

3.0 SIGNIFICANCE OF STUDY

This study will compare and determine the most ideal LA solution to activate a labor epidural: lidocaine, bupivacaine, or a combination of bupivacaine plus lidocaine. We hope to determine which solution will provide the fastest onset and best coverage with the fewest side effects such as maternal hypotension and motor blockade. This will allow anesthesiologists to select a LA

solution that will provide the best analgesic properties (quick onset and adequate spread for labor analgesia) with the fewest side effects (hypotension and motor weakness).

4.0 OBJECTIVE(S) & HYPOTHESIS

Our overall goal is to determine which commonly used LA or combination of LA demonstrates the most ideal properties in a patient receiving an epidural for labor pains. As anesthesiologists, we strive to provide a fast-acting and safe anesthetic in these patients to elicit rapid pain relief in laboring mothers.

Currently, there are several ways in which we activate a labor epidural with LA. Three of the more common LA solutions used are 1% lidocaine, 0.125% bupivacaine, or a combination of bupivacaine and lidocaine. In a prospective, randomized, double-blinded study, we plan to determine if one solution is more superior to the others.

Briefly, after consent is obtained, a standard anesthesia provider will place a labor epidural in regular fashion. After a negative test dose, the anesthesia provider will then administer the study solution the patient was randomized to receive (10 mL of 0.125% bupivacaine, 10 mL of 1% lidocaine, or 5 mL of 0.125% bupivacaine plus 5 mL of 1% lidocaine). The standard epidural infusion bag will then be started by the anesthesia provider. Both the patient and investigator will be blinded to the study. Once the study drug bolus has been given, the investigator will collect the data.

Data to be collected will be: sensory level (by pin prick and ice), degree of motor block by using a modification of Bromage's scale³ (see section 8.0), maternal heart rate (HR) and blood pressure (BP), the need to administer a vasopressor agent (phenylephrine or ephedrine) to treat hypotension, the amount of vasopressor given, and fetal heart rate (FHR). Starting with the initial bolus (Time 0 or T₀), data will then be collected 5, 10, 15, and 20 minutes after the bolus.

The primary outcome for this study is the time it takes to achieve a T₁₀ dermatome level by pinprick (which signifies an adequate epidural level for labor analgesia).

Secondary outcomes include: the total spread (both cephalad and caudal) of the LA (dermatome level to be determined by pin prick and ice), degree of motor block, incidence of maternal hypotension defined as a BP >20% decline from baseline, the need to administer a vasopressor to treat the hypotension, the amount given, and if there is any change in fetal status by monitoring FHR.

We hypothesize that lidocaine will achieve a T₁₀ level the fastest when compared to bupivacaine and bupivacaine plus lidocaine. The bupivacaine plus lidocaine solution's onset of action will not be significantly faster when compared to bupivacaine. Given the concentration of the bupivacaine, less hypotension and motor block will be present when compared to the lidocaine and bupivacaine plus lidocaine. The bupivacaine plus lidocaine will offer no increased benefit of having a faster onset with less hypotension or motor blockade than either LA solution alone.

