5.0 INTERPRETATION OF EXPECTED RESULTS

06_18_2014

If we see a significant decrease in time to achieve a T₁₀ dermatome level with the bupivacaine and lidocaine mixture compared to the bupivacaine only solution, then that would imply that the addition of the lidocaine did speed up the onset of action of the LA solution we used to activate the epidural. We would also need to account for each LA solution's side effect profile. By measuring the incidence of hypotension and degree of motor blockade, we will be able to determine if one solution's side effect profile is more favorable. By determining the advantages vs. disadvantages of each solution, we would be able to recommend the most ideal LA solution of those studied as the solution best suited for activation of labor epidurals.

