8.0 STUDY INTERVENTIONS/PROCEDURES

Our study will be a prospective, randomized, double-blind study comparing three commonly used methods to activate a labor epidural. These three solutions will be 10 mL of 0.125% bupivacaine (B), 10 mL of 1% lidocaine (L), and 5 mL of 0.125% bupivacaine plus 5 mL of 1% lidocaine (BL). The primary outcome of the study will be measurement of the time it takes to achieve an adequate anesthetic level (T₁₀) to control labor pains. Secondary outcomes include: the total level achieved, degree of motor blockade, incidence of maternal hypotension (>20% decline from baseline), the need for vasopressor use, the amount of vasopressor needed, and fetal

well-being (monitoring of FHR). Since LA will be required to produce our primary outcome, no group will receive a placebo. The three groups (B), (L), and (BL) will be compared to each other.

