Pregnant patients who are admitted to the L&D floor at the WIC and have none of the above mentioned exclusion criteria will be approached about enrolling in the study. Informed consent will be obtained before any obstetric intervention occurs that might cause pain or altered mental status to the patient. Once the patient requests for her epidural to be placed, the investigator will be notified. Any qualified anesthesia provider will then place the labor epidural. Per our routine practice, the epidural will be placed in the L₂₋₃ or L₃₋₄ interspace, secured at plus 5 cm from the loss of resistance distance at the skin, and the routine test dose of 3 mL of 1.5% lidocaine with 1:200,000 epinephrine will be administered to rule out spinal or intravascular placement of the epidural catheter. After the epidural catheter is deemed safe to use (from a negative test dose), the anesthesia provider will administer the LA solution the patient has been randomized to receive: 10 mL (B), 10 mL (L), or 10 mL (BL), and the standard LA infusion will be connected to the epidural and started. The time that the LA bolus occurred will be marked as T₀. The patient's BP, HR, anesthetic level to pin prick and ice, degree of motor blockade, and FHR will be recorded at that time by the blinded investigator. Motor blockade will be tested by a modification of Bromage's scale where: 0 = the ability to maintain a leg lift for prolonged periods; 1 = the ability to lift legs briefly; 2 = the ability to bend knees; 3 = the ability to wiggle toes; 4 = no movement in lower extremities.³ Then at intervals of 5, 10, 15, and 20 minutes, the investigator will document the above mentioned data with the addition of any vasopressor (phenylephrine or ephedrine) required to treat maternal hypotension and the dose.

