11.0 STATISTICAL CONSIDERATIONS

The outcome Y is time to T_{10} sympathectomy. An ANOVA will be used to estimate the overall difference of the mean onset times between study groups. An estimate of onset times of 5, 6 and 7 minutes and an estimated variance of 1 min is based on the existing literature.¹² Using an alpha = 0.05, 80% power and a calculated effect size of $f = 0.82$, the total sample size sample size based on an ANOVA is N=18. Accounting for some prediction inaccuracy, we propose a target sample size of N=45, n=15 per study group.

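### Time to hypotension is promised as a factor in choosing the solution, but it is in no outcome list and has no planned analysis; listing it and adding a continuous blood-pressure measure is a cheap improvement

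*Combined protocol and SAP*

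**What the plan says.** - **Aim.** Section 2.0 (Background & Rationale) lists what this trial will add to the earlier labor-epidural study. It includes "the time it takes to develop hypotension", sets this apart from overall incidence, and says such factors will matter in finding the best solution.
- **Outcome lists.** Section 1.0 has "incidence of hypotension and need for vasopressor therapy". Section 4.0 has "incidence of maternal hypotension defined as a BP >20% decline from baseline". Section 8.0 has "incidence of maternal hypotension (>20% decline from baseline), the need for vasopressor use, the amount of vasopressor needed". None mentions timing. The word onset in the section 1.0 list belongs to motor block.
- **Analysis.** Section 11.0 plans one: "An ANOVA will be used to estimate the overall difference of the mean onset times between study groups". It does not mention hypotension.
- **Use of the result.** Section 5.0 (Interpretation of Expected Results) says: "By measuring the incidence of hypotension and degree of motor blockade, we will be able to determine" whether one side-effect profile is more favorable. This feeds the recommendation.
- **Data.** Sections 4.0 and 8.0 schedule blood pressure (BP) at the bolus (T0) and at 5, 10, 15 and 20 minutes, with vasopressor use and dose. The T0 values "will be recorded at that time by the blinded investigator". Before T0, "the routine test dose of 3 mL of 1.5% lidocaine with 1:200,000 epinephrine will be administered".

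**The concern.** The protocol presents timing of hypotension as something the trial will add and as an input to the recommendation. An analyst who follows the outcome lists and section 11.0 would never produce it. What would be produced is a yes/no count in 15 patients per arm, which discards both when the fall occurred and how deep it was. At stake is a stated question left unanswered although the readings exist, and a side-effect comparison less informative than the same data allow.

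A smaller gap is that no section says whether BP means systolic or mean, or which reading is the baseline for the 20% fall.

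**Working it through.** **1. The plan's own figure.** Section 11.0 uses means of 5, 6 and 7 min and variance 1, so f = sqrt(((5−6)² + 0 + (7−6)²)/3) = sqrt(2/3) = 0.816, stated as 0.82. With noncentrality N·f², N = 18 gives power 0.809 at f = 0.82 and N = 15 gives 0.705. The stated N = 18 reproduces. The target of 45 (15 per arm) derives from this onset-time calculation; no figure is stated for hypotension.

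**2. Assumptions.** The documents give no hypotension rates and no BP variability. Four pairs of rates are assumed: 10 v 30, 20 v 40, 10 v 40 and 10 v 60%, with n = 15 per arm and two-sided alpha 0.05.

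**3. Incidence.** Power is the sum of the binomial probabilities of all 16 × 16 possible results that the test rejects.

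**4. Largest percentage fall.** If falls are normal with equal SD in both arms, an incidence p above the 20% cut fixes the mean, and the standardized difference is d = z(p2) − z(p1). For 10 v 30%, d = −0.524 + 1.282 = 0.757 (unrounded z values). The other pairs give 0.588, 1.028 and 1.535. Power comes from the noncentral t with 28 df and noncentrality d·sqrt(15/2), without adjustment for baseline BP.

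| Rates | Fisher | Chi-square (uncorrected) | Continuous |
|---|---|---|---|
| 10 v 30% | 15% | 28% | 52% |
| 20 v 40% | 11% | 23% | 34% |
| 10 v 40% | 33% | 51% | 78% |
| 10 v 60% | 74% | 88% | 98% |

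With Bonferroni over the three pairs (alpha 0.05/3):

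| Rates | Fisher | Chi-square | Continuous |
|---|---|---|---|
| 10 v 30% | 5% | 15% | 34% |
| 20 v 40% | 5% | 11% | 19% |
| 10 v 40% | 16% | 33% | 61% |
| 10 v 60% | 60% | 74% | 94% |

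The chi-square column here matches the Fisher column of the first table to three decimals. That is not a misprint.

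**5. Time to hypotension.** A log-rank test on four 5-minute intervals with constant hazard (20,000 simulations) has power 27, 23, 49 and 87%, about the same as chi-square on incidence. At 10% incidence an arm expects 15 × 0.10 = 1.5 events and has none with probability 0.9^15 = 0.21. Timing answers the stated question but adds no real power, so it should be descriptive.

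**6. What an interval shows.** With 3/15 in both arms, the Wilson limits for each are 0.070 and 0.452. Newcombe's 95% interval for the difference is ± sqrt((0.2 − 0.070)² + (0.452 − 0.2)²) = ± 0.283, or −28 to +28 points.

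**7. Readings after vasopressor.** This was simulated with four equally correlated normal readings (correlation 0.5 to 0.9), treatment only after the first reading beyond the cut, and that reading kept. Dropping later readings shrinks the mean difference between arms by about 4 to 10%, with almost no loss of power.

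**The case against.** The other side has a good case on several points.

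- **The gap is small.** Section 4.0 says that secondary outcomes include those listed, which need not be exhaustive, and the readings will exist. Section 11.0 gives no analysis for any secondary outcome. All true, but timing is the hypotension question section 2.0 singles out, and it is in none of the three lists.
- **Low power is not an error.** A reader might infer that the trial was wrongly sized for hypotension. The documents do not support that: no power is claimed for hypotension, and 45 was set from onset time. Low power is a limitation that confidence intervals will show.
- **Section 5.0 can be over-read.** A reader might infer that it treats a non-significant difference as evidence of similarity. It does not say so. It says only that the measurements will show whether one profile is more favorable.
- **Baseline has a natural reading.** T0 is the only scheduled study BP before the 5-minute one. Section 8.0 also judges the heart-rate response to the test dose against a baseline, which must precede that dose, but this is a safety criterion for another variable. A reader might infer that the unlabelled baseline biases the comparison. The test dose is the same in all arms, so the choice of reading changes the level of incidence and does not by itself bias the difference.
- **The continuous measure is partly a preference.** It answers a different question from a fall above 20%, and its gain rests on normality and equal SD for what is really the largest of four readings. This stands, so it should support incidence and not replace it.

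**Conclusion.** The point holds as a specific, inexpensive improvement. One aim in section 2.0 has no counterpart in the outcome lists or the analysis section, although the data for it are collected. Adding a continuous analysis of the same readings raises power from 15, 11, 33 and 74% (Fisher) or 28, 23, 51 and 88% (chi-square) to about 52, 34, 78 and 98%. The continuous measure stays ahead after Bonferroni. In three of the four scenarios it is still below 80% without that correction, so it improves a secondary comparison and does not make it definitive.

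The sizes depend on assumed rates and on normal falls with equal SD. That timing is promised and then dropped depends on neither. The BP component and baseline are missing detail to be clarified. They are not grounds for doubting the comparison between arms.

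**What to change.** 1. In sections 1.0, 4.0 and 8.0, list time to first BP fall above 20%, on the 5-minute grid and censored at 20 minutes, as a descriptive secondary outcome with curves by arm.
2. In section 11.0, keep incidence and report it by arm with the three pairwise differences and 95% confidence intervals. Add, as a supportive analysis, the largest percentage BP fall as a continuous measure adjusted for baseline BP, with and without readings after vasopressor.
3. As a clarification, state whether BP is systolic or mean and that baseline is T0 (or another named reading), and use that choice for incidence, timing and the continuous measure.

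**Cost.** Wording and a little analysis. BP, vasopressor use and dose are already recorded, and the primary analysis is unaffected. The downsides are one more secondary comparison and the influence of vasopressor on later readings, which is why both versions are reported. A baseline before the test dose would need one extra field, because scheduled readings start at T0. Section 9.0 says hypotension is also treated with fluid, which is not among the recorded data, so only vasopressor can be handled unless a field is added.

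### Blood pressure is read five times per patient but judged only as a yes/no 20% fall; a baseline-adjusted numeric comparison should be added beside it

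*Combined protocol and SAP*

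**What the plan says.** - **Measurement.** The summary (1.0) has the investigator assess "blood pressure, heart rate, and fetal heart rate at intervals of 0, 5, 10, 15, and 20 minutes". Section 4.0 agrees on the post-bolus times: "data will then be collected 5, 10, 15, and 20 minutes after the bolus". Section 8.0 places the first reading at the bolus itself: "The patient's BP, HR, anesthetic level to pin prick and ice, degree of motor blockade, and FHR will be recorded at that time". Each woman therefore has one T0 value and four later ones.
- **Outcome.** Section 4.0 lists "incidence of maternal hypotension defined as a BP >20% decline from baseline". Section 8.0 repeats it as "incidence of maternal hypotension (>20% decline from baseline), the need for vasopressor use, the amount of vasopressor needed". Neither section says whether BP means systolic, mean or diastolic, or which reading is the baseline.
- **Related items.** The background (2.0) says the study will look at "the time it takes to develop hypotension" and not only at overall incidence. That aim appears in no outcome list and has no analysis. Section 4.0 also lists "the need to administer a vasopressor to treat the hypotension, the amount given".
- **Use.** The section on interpretation of expected results (5.0) states that, by measuring hypotension incidence and motor block, "we will be able to determine if one solution's side effect profile is more favorable". This is then weighed with onset in choosing a solution to recommend.
- **Analysis.** Section 11.0 deals only with time to T10. It names no test and gives no power for hypotension.

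**The concern.** With a yes/no cut at 20%, a 19% fall counts as no fall and a 21% fall counts the same as a 40% fall. With 15 women per arm, that makes a weak comparison of a quantity that was measured as a number.

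The protocol hypothesises less hypotension with bupivacaine and no overall advantage for the mixture (4.0). If the incidence comparison has low power, a real difference in BP fall may well come out as non-significant. For the mixture, such a result would look like confirmation of what was predicted, and a solution could be recommended as equally safe on evidence that could not have shown otherwise.

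**Working it through.** **1. The plan's own figure.** Section 11.0 gives means of 5, 6 and 7 minutes and variance 1. The SD of the three means is √(2/3) = 0.816, so f ≈ 0.82. One-way ANOVA power (noncentral F, 3 groups, noncentrality N·f², alpha 0.05) is 70.5% at N=15 and 80.9% at N=18. The stated N=18 is reproduced, and N=45 gives 99.9%. This concerns onset time only; the documents give no corresponding figure for hypotension.

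**2. Inputs for hypotension.** From the documents: 15 per arm and alpha 0.05 (which 11.0 states for the primary outcome only). Assumed, because the documents do not give them: the hypotension rates, shown below as a range, and a BP fall that is normally distributed with equal SD in the two arms. On that model, rates p1 and p2 at a common cut-off correspond to a mean difference of d = z(p2) − z(p1) in SD units. For 10% vs 40%, d = −0.253 − (−1.282) = 1.03.

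**3. Pairwise power, two-sided 0.05, no multiplicity adjustment.** The yes/no figures sum the binomial probabilities of all tables that each test rejects. The numeric figure is the noncentral t with 28 degrees of freedom and noncentrality d·√(15/2); for d = 1.03 this is 2.82.

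| Assumed rates | d (SD) | Fisher | Uncorrected chi-square | t-test on the fall |
|---|---|---|---|---|
| 10% vs 30% | 0.76 | 15% | 28% | 52% |
| 10% vs 40% | 1.03 | 33% | 51% | 78% |
| 20% vs 40% | 0.59 | 11% | 23% | 34% |
| 20% vs 50% | 0.84 | 25% | 42% | 60% |
| 30% vs 60% | 0.78 | 23% | 37% | 54% |

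**4. The same gap as a sample size.** For 10% vs 40% at 80% power:
- yes/no: (1.96·√(2·0.25·0.75) + 0.842·√(0.09 + 0.24))² / 0.3² = 31.5, so 32 per arm;
- numeric: 2·(1.96 + 0.842)² / 1.03² ≈ 14.8, so 15 per arm.

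Across eight rate pairs (the five above plus 5% vs 20%, 10% vs 50% and 10% vs 60%), yes/no needs 1.6 to 3.0 times as many patients. At 15 per arm, 80% power for yes/no requires about 10% vs 56% or 20% vs 69% (normal approximation).

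**5. Information kept by the cut.** For one normal value cut so that a proportion p are events, the large-sample efficiency is φ(c)² / [p(1−p)], where c = z(1−p). At p = 0.05: 0.1031² / 0.0475 = 22%. At 0.10: 34%. At 0.20: 0.2800² / 0.16 = 49%. At 0.30: 58%. At 0.40: 62%. At 0.50: 0.3989² / 0.25 = 64%. The loss therefore runs from 36% to 78%, and passes one half only at an incidence of about 20% or lower. Any further loss from ignoring the repeated readings cannot be computed, because the documents give no SD or correlation.

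**6. Does vasopressor treatment remove the gain?** This was simulated with assumed values: baseline 120 mmHg, SD 12 mmHg, and the lowest reading up to the first vasopressor analysed by ANCOVA on T0 BP.
- Mean falls of 6 and 16 mmHg, correlation between readings 0.4 to 0.8, and 0 to 100% of below-threshold readings treated: ANCOVA power 80% to 99%, Fisher 35% to 50%. ANCOVA type I error was 4.2% to 4.5%.
- Smaller differences: ANCOVA power about 50% for falls of 6 vs 12 mmHg and 48% for 10 vs 16 mmHg.

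**The case against.** Several objections have force.

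- **The cut is not the only use of BP.** Time to hypotension is an aim in 2.0, and vasopressor need and amount are listed outcomes that say something about severity. This stands as description. However, time to hypotension still rests on hypotension as an event and has no analysis, and vasopressor use records treatment, not the size of the fall.
- **Fisher flatters the contrast.** The protocol names no test, and Fisher is conservative at this size. This stands in part: for 10% vs 40%, power rises from 33% to 51% with an uncorrected chi-square. The remaining gap to 78% comes from the cut.
- **Three pairwise comparisons raise multiplicity.** With a Bonferroni correction, t-test power falls to 34% (10% vs 30%), 61% (10% vs 40%) and 42% (20% vs 50%). This stands, so the plan should say how multiplicity is handled; correcting would lower the yes/no power as well.
- **Treatment contaminates later readings.** Section 9.0 also treats hypotension with crystalloid, which is not among the data to be collected. Stopping at the first vasopressor does not remove that effect. Treated women also contribute fewer readings to their minimum, which can shrink the difference. This stands, and makes the numeric powers upper figures.
- **A fall above 20% is the clinically meaningful event.** Replacing it would change the question. This stands against replacing it, but not against adding a numeric analysis beside it.
- **The wider gap is that 11.0 specifies no analysis for any secondary outcome.** That is true. It does not remove this point, since naming a test for the incidence would leave the loss of power in place.

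**Conclusion.** The concern holds as a weakness in a secondary outcome that the recommendation explicitly uses. It does not touch the primary sample size. At 15 per arm and the assumed rates, the yes/no comparison has 11% to 33% power by Fisher or 23% to 51% by chi-square, against 34% to 78% for the fall analysed as a number. These figures rest on assumed rates, normality, equal SD and no multiplicity adjustment.

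Three stronger readings are tempting and are not supported:
- *That the cut throws away most of the information.* This depends on an incidence the documents do not give. At 30% to 50% incidence the loss is 36% to 42%.
- *That hypotension alone decides the recommendation.* The section on interpretation of expected results weighs it with motor block and onset time.
- *That a numeric analysis would usually find a real difference.* Power is only 34% at 20% vs 40%, and about 50% in the simulation of 6 vs 12 mmHg. The gain is real but does not make the trial well powered for small differences.

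**What to change.** Keep the incidence of a fall above 20% as the clinical secondary outcome. Add to 4.0, 8.0 and 11.0:

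1. A prespecified supporting comparison of the lowest BP at the 5 to 20 minute readings, up to and including the reading at first vasopressor, by ANCOVA with T0 BP as covariate. Report the three between-arm differences with 95% confidence intervals and state how multiplicity is handled.
2. One named BP component, and a statement of which reading is the baseline for the 20% rule.
3. A sensitivity analysis ranking the largest percentage fall, with vasopressor-treated women ranked worst.
4. A sentence that a non-significant incidence comparison will not be interpreted as equal safety.

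The cost is a few sentences and a little more analysis. It needs no extra patients or BP readings. The limitation to state is that vasopressor or unrecorded crystalloid can blunt later readings, so the power gain shown here is the most that could be expected.
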